10.2.2 Causality Rating	26
10.2.3 Severity of ADE	26
10.3 Reporting	26
11. Study Key Personnel	26
CHKD Principal Investigator: [name] [name]., FAAP	26
Woebot Liaison: [name].	27
Woebot Liaison: [name].	27
CHKD Sub-Investigator: [name], D.O.	27
CHKD Co-Investigator: [name]. CONFIDENTIAL	27 5

Woebot Health	Version 5.0
W-GenZD-003	31 May 2023
References	28
Appendix 1. Parental Check-In Guidance	31
Appendix 2. Unscheduled Telephone Visit: Safety Response Follow-Up	32

Version 5.0 31 May 2023

Table 1. Schedule of Events

	Screenin	ng Period		Treatment Per	iod	Follow	v-Up Period
Visit Weeks/Days	Screening Day -7 to -1	Baseline Day 0	Visit 2 Day 5 (+2)	Visit 3/Week 2 Day 14(+6)	Visit 4/ Week 4 (EOT) Day 28 (+6)	Visit 5/ Week 6 Day 42 (+6)	Visit 6 Week 8 (EOS) Day 56 (+6)
		_					
Informed Consent/Assent	Х						
Demographics ^{c, d}	Х						
Psychiatric History ^{c, d}	Х						
Prior & Concomitant Medications/Therapy ^d	Х				Х		
CHKD Brief Clinical Needs Assessment Information ^d	Х						
Eligibility Confirmation (Inclusion/Exclusion)	Х						
Randomization		Х					
Download Study Application ^a		х					
PHQ-8 ^b		Х		Х	Х		Х
GAD-7 ^b		Х			Х		Х
MFQ ^b		Х			Х		Х
WAI-SR ^b			Х		Х		
CSQ-8 ^b					Х		
Satisfaction Questionnaire ^a					Х		
UPRI ^b					Х		
App Engagement Metrics (W-GenZD only)					Х		
Weekly teletherapy Group Attendance (CBT-lite				v			
only) ^d				^			
Parental Check-Ins (Telephonic)				х	х	х	Х
SNP/Safety Response ^e				Х			
Healthcare Utilization ^{c, d}							Х
Assessment of AE/SAEs				Х	Х	Х	Х
Termination of W-GenZD and Teletherapy Access					Х		
Participant and Parent/Guardian Exit Interviews ^f							X

Woebot Health W-GenZD-003 Version 5.0 31 May 2023

^a W-GenZD participants only, ^bSelf-Report Clinical Assessment (adolescent), ^c Parent/Guardian Questionnaire, ^dCollected from CHKD system, ^e A SNP or Safety event will trigger an unscheduled visit from ICF to EOS, see section 5.6, ^fOptional study procedure; EOS = End of Study; EOT = End of Treatment; SNP=Safety Net Protocol

Protocol Synopsis

Study Device	W-GenZD		
Protocol Number:	W-GenZD-003		
Protocol Title:	A Randomized Controlled Trial of the Feasibility and Acceptability of W-GenZD versus CBT-lite teletherapy for Adolescents seeking Mental Health Services		
Main Criteria for Inclusion:	 Inclusion Have completed triage at CHKD and have been deemed appropriate for the low-intensity intervention track, given presenting problem(s) of depressive or anxiety symptoms Adolescent 13-17 years of age, inclusive U.S. Resident Both adolescent participant and parent/guardian are able to read and write in English Own or have regular access to a smartphone (Android or iOS smartphone with a recent, supported operating system), that can receive SMS messages, and reliable Wi-Fi access or sufficient data to engage with assigned treatment condition for the duration of the study If currently prescribed antidepressant medications (e.g. escitalopram/Lexapro, fluoxetine/ Prozac), antipsychotic medications (e.g. aripiprazole, asenapine, olanzapine, paliperidone, quetiapine, risperidone), or stimulants (e.g. amphetamine/Adderall, Methylphenidate/Ritalin) and alpha agonists (e.g. atomoxetine/Strattera, Guanfacine/Intuniv) they are at a regular, stable dose for at least 60 days at screening Not currently actively engaged is psychotherapy 		
	 8-week duration. 9. Family is willing and able to engage in discussion of safety planning in the event of suicidal symptoms 		

	Exclusion		
	 Lifetime diagnosis of a psychotic disorder (including schizophrenia or schizoaffective disorder) 		
	2. Lifetime diagnosis of bipolar disorder		
	3. Lifetime diagnosis of autism spectrum		
	disorder or pervasive developmental disorder (e.g. autism, Asperger syndrome, Rett's syndrome)		
	 Current diagnosis of developmental delay or intellectual disability 		
	5. Suicidal ideation with a plan or intent or a		
	suicidal attempt within the past 12 months		
	6. History of (a) drug and/or alcohol abuse		
	within the past 12 months		
	 Current use of benzodiazepines (e.g. lorazepam, clonazepam, alprazolam, diazepam, triazolam) or certain sleep aids (zolpidem, eszopiclone, zaleplon) 		
	8. Previous Woebot application use		
	 Enrollment of more than one member of the same household 		
Study Primary Objective:	What is the feasibility and acceptability of W-GenZD among a group of adolescents and who have been screened and triaged into low-intensity treatment within CHKD?		
Study Design:	This study will be a randomized controlled trial of W-GenZD versus fcpton The trial will consist of 3 primary phases: Screening/Baseline, Treatment, and a Follow-up period.		
Treatment Regimen:	W-GenZD: 5-10 minutes of daily use recommended Teletherapy CBT Groups: 1 group/week of treatment period		
Duration of Study Participation:	8 weeks		
Number of Participants:	260 participants		
Number of Sites:	1		
Primary Endpoints:	 Primary Feasibility and Acceptability outcomes at 4-weeks: Usage Rating Profile Intervention (URPI)-Feasibility and URPI-Acceptability Client Satisfaction Questionnaire (CSQ-8) 		
	Additional feasibility and acceptability metrics:		

	 App engagement metrics (W-GenZD condition) Content/Program satisfaction ratings (both conditions) Group attendance (CBT-lite teletherapy condition) Qualitative findings about the participant experience, based on interviews with a self-selected subset of participants (adolescent and parent/guardian)
Secondary Endpoints:	 Patient Health Questionnaire for Teens (PHQ-8) total score Generalized Anxiety Disorder Questionnaire (GAD-7) Mood and Feeling Questionnaire (MFQ)
Tertiary Endpoint:	• Working Alliance Inventory-SR (WAI-SR)
Exploratory Endpoints:	 To observe and describe the utilization and outcomes of the safety procedures utilized within this study (Safety Net Protocol, AE/SAEs and device relatedness) Pre-period and study-period healthcare utilization data. This will include: Diagnosis (e.g., ICD code) and service rendered (e.g., CPT code) Emergency Department utilization Primary care utilization (e.g., primary care well visit and sick visit appointment) Behavioral-health related utilization (psychiatry, psychology, other therapist, etc) Psychiatric medication prescriptions Social determinants of health information (e.g., food and housing insecurity and social work utilization) Comorbidity data (i.e., any additional behavioral health or physical health diagnoses) Problem List Any relevant lifetime psychiatric assessments (e.g., Vanderbilt, PHQ)
Interim Report:	Readout of complete baseline sample descriptive stats (demographics, enrollment data, etc) and baseline scores of measures

1. Introduction

1.1 Background

Adolescence is a *unique and critical period* of neurological development. The brain will never be as sensitive to reward nor as plastic as it is during adolescence [1]. It is also the peak time for the onset of most mental illnesses [2]. Mental illnesses that emerge before adulthood carry a 10-fold higher cost than those that emerge in adulthood [3]. With mental illness being the largest and most costly problem to the global economy [4] and depression specifically being the leading cause of disability worldwide [5], the public health impacts are staggering, yet persistently increasing, especially among adolescents [6]. Adolescence is a very vulnerable developmental life stage, in which 50% of lifetime cases of mental illness begin by the age of 14, and 75% by the age of 24 [7]. Depression onset in adolescence also confers high risk for chronic depression recurrence as well as other psychiatric sequelae [8,9].

The American Psychological Association's (APA) [10], American Academy of Pediatrics (AAP) [8], American Academy of Child and Adolescent Psychiatry (AACP), and the National Institutes of Clinical Excellence's (NICE)[11] agree that swift and early intervention of depression in adolescence is a critical part of the standard of care for this population, with all recommending routine screening for depression, particularly in primary care settings [8]. Standard of care treatment recommendations across the board include psychotherapy and/or pharmacotherapy, with APA, AAP and NICE unanimously recommending cognitive behavioral therapy (CBT) and interpersonal therapy for adolescents (IPT-A) as the most evidence-based psychotherapeutic options. Data suggest that combining psychotherapy and an antidepressant medication, particularly for more complicated or severe presentations, may have better outcomes than either treatment alone [12, 13]. Additionally, support in the form of psychoeducation and case management, as well as involvement of family and school throughout the treatment period is also recommended [8, 14, 15].

In practice, there are barriers to implementing these recommendations consistently and thus, as many as two out of three adolescents with depression *do not receive any treatment* [13]. There are only two FDA-approved psychopharmacological options for adolescent MDD, compounded by a dearth of high-quality empirical evidence compared to adult MDD and the potential for serious side effects. Critically, lack of access is consistently a treatment barrier for many adolescents, especially access to clinicians skilled in high-quality psychotherapy and/or pharmacotherapy. This longstanding national shortage of child and adolescent specialty trained providers [13] often leaves the complex management of adolescent depression in the overburdened hands of primary care providers. In addition, many families are reluctant to consider antidepressant medications as first-line treatment for adolescents [16], preferring psychotherapy [17]. Yet, research shows that recommended psychotherapies are seldom used [18, 19]. Persistent barriers to use pertain to access, cost and stigma [11, 20], with the latter discouraging adolescents from seeking help. Additional problems in real-world practice include incomplete use of screening tools even when recommended at the organizational level within a pediatric care network [21], limited guidance on how a clinician should use those routine assessments to inform treatment decisions [22] and concerning racial disparities in rates of treatment and follow-up [23].

Clearly, early and successful intervention is crucial, and yet there have been surprisingly few therapeutic approaches *specifically designed for adolescents*. Up to 75% of young people will never get the care that they need [24] and early dropout is common among those that do [25], suggesting that the structure and systems of traditional clinical settings are ill fitted to adolescent lives. In short, access, broadly defined, remains the most significant barrier to mental health care for young people.

Undoubtedly technology must become part of the solution, as part of an ecosystem of mental health services. However, presently there are no FDA-approved mobile medical devices for the treatment of major depression in adolescence.

1.2 Clinical Experience with Woebot

Woebot is an automated relational agent based on the most researched and scientifically validated psychotherapies, primarily CBT, and accessible via an iOS and Android application. The user experience is centered around mood tracking and goal-oriented, tailored conversations. Users become familiar with Woebot as a friendly, helpful character that is explicitly not a human, nor a therapist. Woebot has been designed with a personality to facilitate a working alliance over time. Daily push-notifications prompt users to check-in with Woebot. Upon opening the app, Woebot asks users what they are doing (context) and how they are feeling (mood). Using proprietary natural language processing (NLP) and artificial intelligence (AI), Woebot is able to understand users in an organic, familiar way and lead them appropriately through a program that is personalized each day, in real-time, to the user's needs.

1.2.1 Randomized Controlled Trial (RCT) of an Early Prototype of W-GenZD in 18-28 year olds

Purpose: To evaluate the feasibility, acceptability, and preliminary efficacy of W-GenZD among a college-based sample (N=70) in an RCT comparing an early prototype of W-GenZD to an information-only control group.

Methods: Participants ages 18-28 years (N = 70) who self-identified as experiencing symptoms of depression and anxiety were randomized to receive Woebot or an e-book on depression published by the National Institute of Mental Health. Outcomes were assessed at 2-weeks end-of-treatment. The study was approved by the Stanford University IRB and published in the Journal of Medical Internet Research (JMIR) [26]. The study was powered for the full 18-28 age range. A post-hoc subgroup analysis was also performed among those participants aged 18-21 years (n=26) to characterize clinical outcomes for this relevant age group specifically.

Key Results: In the broader cohort of all participants ages 18-28 years, those in the Woebot group significantly (F=6.5; p=.01) reduced their symptoms of depression over the study period as measured by the Patient Health Questionnaire (PHQ-9), relative to those in the control group [26]. Participants engaged with the device an average of 12.14 times (SD=2.23; median=12; range 8-18) over the 2-week study period. As it relates specifically to the subgroup of interest, 37% of participants (n=26/70) were ages 18-21 years. Intent-to-treat analysis indicated that Woebot participants ages 18-21 years experienced a reduction in symptoms of depression as measured by the PHQ-9 (mean reduction = 1.7, SD (4.2)), and in symptoms of anxiety as measured by the Generalized Anxiety Disorder (GAD-7) scale (mean reduction = 1.7, SD (3.2)) at 2-weeks, as compared to baseline. Within-subject effect sizes on both measures were small to medium (Cohen's d = .27 and .31 for PHQ-9 and GAD-7, respectively); neither of these differences was statistically significant (t = -1.9, p = .09 and t = -1.4, p = 0.19, respectively) at 2-weeks, relative to baseline, due the limited sample size as the original study was powered for the full 18-28 range. However, the subgroup results show a trend that is consistent with the overall results.

Conclusion: RCT results indicated that W-GenZD was a feasible, effective, and engaging way to digitally deliver CBT to participants self-identifying as having symptoms of depression or anxiety, in the adolescent population ages 18-28. Results in the 18-21 subgroup were consistent with those in the larger study, but were not statistically significant since the study was originally powered for the larger group.

1.3 Rationale

In recent years, there has been an explosion of interest and development of technological solutions to either supplement existing mental health treatments or expand access to quality mental health services. This development was matched by patient demand with about 70% showing interest in using mobile applications (apps) to self-monitor and self-manage their mental health [1]. Internet interventions for anxiety and depression have significant empirical support [2] with outcomes comparable to therapist-delivered cognitive behavioral therapy (CBT) [3-4]. Yet, despite demonstrated efficacy, they are characterized by relatively poor adoption and adherence. One review found a median minimal completion rate (usually defined as completion of ~4 sessions) of 56% [5].

Another problem is that almost all of the research on mobile apps was conducted on apps that are not commercially available. For example, one systematic review of 5,464 abstracts identified just 5 apps that had supporting evidence from randomized controlled trials, and none of them were available commercially [6]. In contrast, apps that were commercially available typically lack evidence and/or a commitment to demonstrate outcomes.

Conversational agents, or chatbots, are software programs that use natural language as inputs and outputs instead of, for instance, menu commands (e.g., File/Save As...) or graphical inputs (e.g., clicking on an icon to open an app). Recent advancements in voice recognition have given rise to the emergence of many conversational agents such as Apple's Siri or Amazon's Alexa. Interacting in this way appears to be a more natural medium through which individuals engage with technology. People respond and converse with nonhuman agents in ways that mirror emotional and social discourse dynamics when discussing behavioral health [7].

Moreover, evidence-based in-person therapies such as CBT, traditionally assign clients opportunities to practice therapy skills outside of sessions, commonly referred to as therapy homework. Historically, it's often proven difficult to engage CBT clients in their homework on a regular basis. Conversational interfaces redefine the entire concept of therapy homework; their ability to be available in the actual moment of need, regardless of time of day or day of week, allows clients to engage with their therapy skills in-vivo, when it matters most.

Children's Hospital of the King's Daughters (CHKD) is a 206-bed, freestanding children's hospital and the heart of an integrated pediatric health care system with roughly 5,000 admissions to the hospital every year. The CHKD mental health program is organized as a stepped care model in which patients are triaged into either low or high-intensity tracks depending on the severity of symptoms, treatment history, and clinical presentation. Due to the demand for adolescent mental health services, the wait time to connect with providers is currently around 3 months. During this waiting period, CHKD offers several teletherapy groups to adolescents and their families seeking services as a support that can be utilized until there is availability.

This protocol aims to demonstrate that Woebot, specifically W-GenZD, is a viable option for this type of healthcare ecosystem.

2. Objectives

Primary Aim: What is the feasibility and acceptability of W-GenZD among a group of adolescents and who have been screened and triaged into low-intensity treatment within CHKD?

- Primary Feasibility and Acceptability outcomes at 4-weeks:
 - o Usage Rating Profile Intervention (URPI)-Feasibility and URPI-Acceptability

- Client Satisfaction Questionnaire (CSQ-8)
- Additional feasibility and acceptability metrics:
 - App engagement metrics (W-GenZD condition)
 - Content/Program satisfaction ratings (both conditions)
 - Group attendance (CBT-lite teletherapy condition)
- Qualitative findings about the participant experience, based on interviews with a self-selected subset of participants (adolescent and parent/guardian)

Secondary Aim: What is the preliminary comparative efficacy of W-GenZD and CBT-lite telehealth zoom groups to manage mood concerns at 4-weeks end of treatment (EOT), relative to baseline?

- Secondary outcomes:
 - Patient Health Questionnaire for Teens (PHQ-8) total score

Tertiary Aim: Investigate potential between group differences on Working Alliance.

- Tertiary outcomes:
 - Working Alliance Inventory-SR (WAI-SR)
 - Generalized Anxiety Disorder Questionnaire (GAD-7)
 - Mood and Feeling Questionnaire (MFQ)

Exploratory Aim: To observe and describe the utilization and outcomes of the safety procedures utilized within this study (Safety Net Protocol, AE/SAEs and device relatedness). To describe the sample population with respect to healthcare utilization, social determinants of health, and comorbidity data for pre-study and during-study (treatment and follow-up) periods and examine associations between these factors and study clinical, alliance, engagement and satisfaction outcomes.

3. Study Population

3.1 Selection of Study Population

Participants are children referred to the CHKD mental health program and are eligible for the low-intensity intervention track. Approximately 30 adolescents are triaged into this low-intensity track per week. In order to be eligible for the low-intensity track, adolescents must *not* meet one or more of the following criteria: have had suicidal ideation within the last 2 weeks or be a current risk to self/others, psychotic presentation, meet criteria for an active eating disorder, history of mania, substance use disorder is the primary clinical problem, is at imminent risk of expulsion, or is currently prescribed 4 or more psychotropic medications.

A minimum of 260 participants (approximately 130 participants/arm) will be enrolled. If participants meet all of the following inclusion criteria and none of the exclusion criteria, they will be randomly assigned to study treatment.

3.1.1 Inclusion Criteria

In order to be eligible to participate in this study, an individual must meet all of the following criteria:

- 1. Have been referred to CHKD Mental Health Program and deemed appropriate for the low-intensity intervention track, given presenting problem(s) of depressive or anxiety symptoms
- 2. Adolescent 13-17 years of age, inclusive
- 3. U.S. Resident

- 4. Both adolescent participant and parent/guardian are able to read and write in English
- 5. Own or have regular access to a smartphone (Android or iOS smartphone with a recent, supported operating system), that can receive SMS messages, and reliable Wi-Fi access or sufficient data to engage with assigned treatment condition for the duration of the study
- 6. If currently prescribed antidepressant medications (e.g. escitalopram/Lexapro, fluoxetine/ Prozac), antipsychotic medications (e.g. aripiprazole, asenapine, olanzapine, paliperidone, quetiapine, risperidone), or stimulants (e.g. amphetamine/Adderall, Methylphenidate/Ritalin) and alpha agonists (e.g. atomoxetine/Strattera, Guanfacine/Intuniv) they are at a regular, stable dose for at least 60 days at screening
- 7. Not currently actively engaged in psychotherapy
- 8. Available and committed to engage with the program and complete assessments for a 8-week duration.
- 9. Family is willing and able to engage in discussion of safety planning in the event of suicidal symptoms

3.1.2 Exclusion Criteria

An individual who meets any of the following criteria will be excluded from participation in this study:

- 1. Lifetime diagnosis of a psychotic disorder (including schizophrenia or schizoaffective disorder)
- 2. Lifetime diagnosis of bipolar disorder
- 3. Lifetime diagnosis of autism spectrum disorder or pervasive developmental disorder (e.g. autism, Asperger syndrome, Rett's syndrome)
- 4. Current diagnosis of developmental delay or intellectual disability
- 5. Suicidal ideation with a plan or intent or a suicidal attempt within the past 12 months
- 6. History of diagnosis of (a) drug and/or alcohol abuse within the past 12 months
- 7. Current use of benzodiazepines (e.g. lorazepam, clonazepam, alprazolam, diazepam, triazolam) or certain sleep aids (zolpidem, eszopiclone, zaleplon)
- 8. Previous Woebot application use
- 9. Enrollment of more than one member of the same household.

3.2 Screen Failures

Participants who sign study assent/consent and do not meet inclusion criteria at Screening, will be considered a Screen Failure. Participants who screen fail will return to the clinical care pathway at CHKD. Re-screens will not be permitted in this study.

3.3 Withdrawal of Participants from the Study

If a participant decides to withdraw consent from the study, they will be removed from all future study activities. In addition, a participant may be withdrawn by the investigator if the participant violates the study plan, or for administrative and/or other safety reasons. Those randomized into the W-GenZD condition will be removed from the study app and program if withdrawn. All data collected prior to withdrawal may be used in descriptive summaries and/or analyses.

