3.3.1 Violation of Study Plan

Participants that do not complete registration for the W-GenZD application or who do not attend a teletherapy group within the first week following randomization will not be removed from the study for failure to access the study intervention. Participants will remain in the study and will continue to receive invitations to complete survey assessments. Depending on randomized condition, those in the CBT-Lite group may attend the remaining sessions (2-4) and those in the W-GenZD group may download the app and program the duration of the 4-week intervention period. All participants randomized to this protocol, regardless of participation or withdrawal status, will be included in the intent-to-treat analysis (see section 9.0).

4. Study Design

This study will be a randomized controlled trial of W-GenZD versus CBT-lite teletherapy groups. The trial will consist of 3 primary phases: Screening/Baseline, Treatment, and a Follow-up period.

All adolescents referred to the CHKD Mental Health Program are provided an orientation about the clinical care program and participate in a brief clinical triage assessment to assess needed level of care. In general, information about the study and consent to contact is included in the welcome packet. As part of recruitment efforts, CHKD may provide families with tokens of engagement (e.g., stress balls). Based on the brief clinical triage assessment, if the adolescent is appropriate for the low-intensity intervention track, study staff will re-introduce the study during the telephone interview and assess the family's (adolescent and parent/guardian) interest in participating. Research staff will follow up with those who expressed interest, present the study, obtain informed consent and assent, facilitate assessment completion, and assess inclusion/exclusion criteria.

Adolescents who do not meet eligibility criteria will be thanked for their interest and willingness to volunteer, and will return to the routine clinical care pathway at CHKD.

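### Section 3.3 does not say that surveys continue after the investigator withdraws a participant, so obtainable Week-4 PHQ-8 scores could be lost, possibly informatively, from the secondary non-inferiority test

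*Combined protocol and SAP*

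**What the plan says.** Section 3.3, which concerns withdrawal from the study rather than from treatment, contains four relevant statements.

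- Withdrawal of consent: "If a participant decides to withdraw consent from the study, they will be removed from all future study activities".
- Investigator withdrawal, at discretion: "a participant may be withdrawn by the investigator if the participant violates the study plan". The same sentence adds administrative and safety reasons, making three grounds.
- A consequence written for one arm only: "Those randomized into the W-GenZD condition will be removed from the study app and program if withdrawn".
- Use of data: "All data collected prior to withdrawal may be used in descriptive summaries and/or analyses".

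Section 3.3.1 is headed as dealing with violation of the study plan, but describes one case: a participant who has not registered for the app, or has not attended a group, in the first week after randomisation. These participants "will not be removed from the study for failure to access the study intervention", and they keep receiving survey invitations. The section ends: "All participants randomized to this protocol, regardless of participation or withdrawal status, will be included in the intent-to-treat analysis".

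Section 9 (Secondary Aim) sets an intent-to-treat non-inferiority test of PHQ-8 at end of treatment (Week 4) with a margin of 2. The only statement on missing data, in the primary-aim analysis plan, is that its amount will be summarised by condition. Further detail is deferred to an SAP; the combined document holds no separate SAP text.

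**The concern.** The plan promises to analyse everyone as randomised, but for one class of participants it does not secure the data to do so. Someone withdrawn by the investigator before Week 4, and then not surveyed, has no observed Week-4 PHQ-8. A method written in the SAP can model or impute that score, but cannot recover it.

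Three features make such gaps potentially informative.

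- What counts as violating the study plan is not defined beyond the first-week exemption. Commitment to engage with the program is an inclusion criterion (Section 3.1.1, item 8), and Section 7 requires no planned medication change. Later disengagement or a medication change could therefore be treated as a violation, and either may track symptoms.
- Withdrawal is discretionary, and an app and a video group cannot be masked from participants or group facilitators.
- The written consequence of withdrawal covers only W-GenZD, so practice may differ between arms.

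Higher PHQ-8 is worse. Losing the worse W-GenZD scores moves the estimated difference towards non-inferiority; losing the worse CBT-lite scores moves it away.

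**Working it through.** **Reading the text.** Does the plan keep surveys going after each event?

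| Event | Surveys afterwards |
|---|---|
| Consent withdrawn (3.3) | Stop, stated |
| No access in first week (3.3.1) | Continue, stated |
| Investigator withdrawal: plan violation, administrative or safety (3.3) | Not stated; only data from before withdrawal are mentioned |

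All three groups belong to the intent-to-treat set. The third row is the gap.

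**Inputs for an illustration of size.** From the documents: about 130 per arm (Section 3.1), 1:1 allocation (Section 4), margin 2 at Week 4 (Section 9). Not in the documents, and so assumed: PHQ-8 SD 5; one-sided alpha 2.5%; a share w = 5%, 10% or 15% withdrawn by the investigator; withdrawn participants d = 4 points worse at Week 4 than those who stay; completers only analysed. The plan gives no derivation of 260 and no withdrawal rate, so there is no figure of its own to reproduce here.

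**Formulas.** Take the true W-GenZD deficit to be exactly 2, so that a claim of non-inferiority is false.

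- SE = SD × √(2/130) = 5 × √(2/130) = 0.620
- Shift in an arm's completer mean = w × d
- Losses in W-GenZD only: P(false non-inferiority) = Φ(w·d/SE − 1.96)
- Losses in CBT-lite only: Φ(−w·d/SE − 1.96)
- Same w and d in both arms: the shifts cancel, giving Φ(−1.96) = 2.5%

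| w | Shift | Shift/SE | W-GenZD only | Both arms equally | CBT-lite only |
|---|---|---|---|---|---|
| 5% | 0.2 | 0.322 | 5.1% | 2.5% | 1.1% |
| 10% | 0.4 | 0.645 | 9.4% | 2.5% | 0.5% |
| 15% | 0.6 | 0.967 | 16.0% | 2.5% | 0.2% |

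The shifts are 10%, 20% and 30% of the margin.

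**Lost sample size.** With SE = 5 × √(1/130 + 1/(130(1 − w))), the W-GenZD-only column becomes 5.0%, 9.1% and 15.1%. Ignoring the lost participants changes little.

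**Sensitivity to the assumed SD.** For W-GenZD-only losses of 5-15%, with n held at 130 per arm, SD 4 (SE 0.496) gives 6.0-22.6% and SD 6 (SE 0.744) gives 4.5-12.4%.

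**Sensitivity to the assumed gap.** With SD 5, w = 10% and the lost n allowed for, d = 2, 3 and 5 give 5.0%, 6.8% and 12.0%.

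**The case against.** Two stronger readings are tempting, and the text supports neither.

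- A reader might infer that investigator withdrawal expressly ends follow-up. Removal from all activities is written only for withdrawal of consent. For investigator withdrawals it is an inference, though a natural one, given the heading of Section 3.3 and its reference only to earlier data.
- A reader might infer that Sections 3.3 and 3.3.1 contradict each other. They do not. Section 3.3.1 is a subsection that exempts one situation from the general discretion, in both arms, and so reduces missing data. Including withdrawn participants in an intent-to-treat set is standard.

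Other points on that side also carry weight. No adherence threshold triggers removal: app use is recommended or encouraged, and late starters may still join. Removal of poor adherers is therefore possible under the wording, not prescribed. PHQ-8 is also taken at baseline and Week 2, and earlier data may be used, so a participant lost before Week 4 could still contribute to a repeated-measures model; none is specified, but none is ruled out. The test is secondary and described as an initial one, while the primary aim is descriptive. The SAP may specify missing-data handling. Finally, the 5-16% range describes losses confined to W-GenZD; with equal losses the bias vanishes, and with losses only in CBT-lite the test becomes conservative.

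What remains is that surveys after investigator withdrawal are left unspecified, the grounds are open-ended, and scores that could be collected at little cost may not be.

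**Conclusion.** The point holds as an avoidable risk to a secondary analysis. The documents do not show that informative gaps will occur, how many participants would be withdrawn, or from which arm. Under the stated assumptions, the false non-inferiority rate could lie anywhere from about 0.2% (15% lost from CBT-lite only), through 2.5% (equal losses), to about 16% (15% lost from W-GenZD only). The upper end should not be quoted without its conditions: one-arm losses, a 4-point gap, SD 5, one-sided 2.5% and a completer-only analysis. The descriptive design of the primary aim limits the importance, but the remedy is cheap and has to be in the protocol, because it concerns whether the scores are collected at all. The change should be made; it is not critical to the trial's main conclusion.

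**What to change.** In Section 3.3:

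1. State that only withdrawal of consent or assent ends data collection.
2. State that participants whom the investigator withdraws for plan violation or administrative reasons stay on the existing Week 2, 4 and 8 survey schedule in both arms, as Section 3.3.1 already provides for first-week non-starters.
3. State explicitly whether surveys continue after a withdrawal for safety reasons. That decision is the sponsor's and investigator's; the text should simply not be silent.
4. Record the date and reason for each withdrawal and report them by arm.

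It would also help to say what violating the study plan means beyond the case in Section 3.3.1, and to confirm that the SAP gives a method, with sensitivity analyses, for Week-4 scores that are still missing.

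Cost: a protocol wording change and some extra survey reminders. The assessments are already scheduled and collected by self-report on a survey platform.
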